13.0 Study Timeline (optional)

	Pre-Screening	Visit 1	Visit 2	Visit 3	Six week Follow up
Estimated time requirement of visit					
Data Collection					
Study Procedure 1					
Study Procedure 2					
Study Procedure 3					
Phone Call Questionnaire					

14.0 ClinicalTrials.gov Information

Directions: If this study has been registered on ClinicalTrials.gov, provide the ClinicalTrials.gov identifier and the investigator/sponsor responsible for registering. If this study has not been registered on ClinicalTrials.gov, provide the rationale as to why and if/when it will be. If it does not meet the requirement for being registered on ClinicalTrials.gov, please state that.

N/A this is not a clinical trial

15.0 List of Data to be Collected

1. Indicate what identifiers you will collect

Name

- Address (e.g., Zip code, other geographical designation, etc.)
- Dates related to an individual (e.g., Date of admission, birth, surgery, etc.)
- Telephone number
- Fax number
- Email address
- Social security number
- Medical record number
- Health plan beneficiary number
- Account number
- Certificate/license number
- Any vehicle or other device serial
- Device identifiers or serial numbers
- Web URL
- Internet protocol (IP) address
- Finger or voice prints (includes audio recordings)
- Photographic images (includes video recordings)
- Other: Any characteristic that would uniquely identify the individual
If other, please explain: [Click here to enter text.](#)

2. List all other data to be collected for the research study. Attach all data collection tools on the Local Site Documents page of the SpartaIRB smart form (Other Attachments). [Click here to enter text.](#)

16.0 Data Analysis Plan

Directions: Describe the data analysis plan, including any statistical procedures. If applicable, provide a power analysis, and study/safety endpoints. Aim 1: Descriptive statistics will be computed for all demographic and multi-item scales. These variables will be used to describe the sample. Study variables will be examined for marked skewness, outliers and systematic missing data. Cronbach's alphas will be computed for the multi-item scales for the full sample and separately by gender, race/ethnicity, age, and T1D duration. Aims 2-3: Correlations between sleep health, diabetes self-management, and symptoms will be assessed. Variables with a modest relationship ($r \geq .3$) will be included in a linear regression analysis. A linear regression will be run where the IV is diabetes self-management, and the DVs are glycemic control. Possible covariates will be determined. Path analysis will be done to test the mediational hypothesis (sleep health variables or distress (general and diabetes) and physical (diabetes) will mediate the effect of diabetes self-management on glycemic control) the following regression equations will be run (Baron & Kenny, 1986): To test the mediation model, the independent variable (diabetes self-management) must affect the mediator (sleep quantity, quality, or timing) in the first equation; next, the independent variable (diabetes self-management) must affect the dependent variables (glycemic control) in the second equation; and lastly the mediator (sleep quantity, quality, or timing) must affect the dependent variables in the third equation. Mediation is present if the independent variable (diabetes self-management) has no effect when the mediator (sleep quantity, quality, timing) is controlled (Baron & Kenny, 1986). Power analysis: A moderate effect size with two predictors (0.13) and 4-5 covariates would require a sample size of 150-200 participants based on a G*power 3.1 calculation. Aim 4:

We will engage 10 emerging adults and use think-aloud interviews where we will ask participants to think out loud about the program as it is delivered. An RA will prompt them to think out loud and audio record the session. We will code the data for themes using qualitative **content analysis**. The expected outcome of aim 4 is to identify barriers and facilitators of the proposed intervention and a protocol for the next phase of the study.

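### Aim 3 asks how much variance sleep adds, but section 16.0 plans no added-variance analysis, and its same-data r ≥ .3 entry rule cannot give a sound estimate of one

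*Protocol*

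**What the plan says.** Protocol section 2.0 sets Aim 3 as a question about added variance. It names four sleep dimensions as alternatives and three outcome domains: symptoms, diabetes self-management and glycemia. The same section defines glycemia as both glycemic control and glucose variability.

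Section 16.0 treats Aims 2 and 3 together, in four steps:

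- Correlations: "Correlations between sleep health, diabetes self-management, and symptoms will be assessed". Glycemia is not in this list.
- Entry rule: "Variables with a modest relationship" (r ≥ .3) "will be included in a linear regression analysis". The outcome of that regression is not given in the sentence.
- A named regression: "A linear regression will be run where the IV is diabetes self-management, and the DVs are glycemic control". On covariates: "Possible covariates will be determined".
- Mediation by the Baron and Kenny steps. Self-management must first affect sleep. Next, self-management "must affect the dependent variables (glycemic control) in the second equation". Lastly, "the mediator (sleep quantity, quality, or timing) must affect the dependent variables in the third equation".

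The power statement reads "A moderate effect size with two predictors (0.13) and 4-5 covariates would require a sample size of 150-200 participants". It gives no test, alpha or power.

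The SAP plans GEE for change from baseline in an intervention and a control group, with 40 completers. It contains no analysis of the cross-sectional aims.

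**The concern.** An aim about additional variance needs a base model, a model with sleep added, and a statistic comparing the two, for each outcome. Section 16.0 names no such pair and no change in R-squared.

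The entry rule raises a second problem. It picks variables by the size of their correlation in the study data; no separate screening sample is described. A sleep measure with a real but smaller contribution is then usually recorded as contributing nothing, while a measure that passes tends to show an exaggerated correlation. Either way, the quantity that Aim 3 asks for is distorted in whichever model the rule feeds.

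At stake is the regression answer to Aim 3. Aim 2 is less affected, because the correlations are to be assessed anyway.

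**Working it through.** **1. Aim 3 outcomes against the written models**

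| Aim 3 outcome | Written model with sleep as predictor | Added-variance statistic |
|---|---|---|
| Symptoms | None clearly stated | None |
| Self-management | None clearly stated; mediation equation 1 runs from self-management to sleep | None |
| Glycemic control | Mediation equation 3 (self-management plus sleep) | None planned; derivable from equations 2 and 3 if fitted on the same people |
| Glucose variability | Not named | None |

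**2. Does the power statement imply an increment test?** Noncentral F, λ = f²N, 6–7 predictors in total, alpha .05 assumed. The document does not say whether 0.13 is f² or R²; as R², f² = .13/.87 = .149.

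- Two-predictor increment, 80% to 95% power: N = 78 to 122 (0.13 as f²) or 68 to 107 (as R²). At 99% power: 168 or 147.
- Overall test of 6–7 predictors at 95% power: N = 167–176 (f²) or 147–154 (R²).

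The stated 150–200 fits an overall test at 95% power, or an increment test at 99%. It cannot show which was meant.

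**3. The entry rule against significance.** Critical |r| = t/√(N − 2 + t²). At N=200, t = 1.972, so 1.972/√(198 + 3.889) = .139. At N=300 it is .113.

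The chance that a sample correlation passes is P = 1 − Φ{[atanh(.3) − atanh(ρ)]·√(N − 3)}. For ρ = .20 and N=200: (.3095 − .2027) × 14.04 = 1.50, so P = .067.

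| Assumed true r | .20 | .25 | .30 | .35 | .40 |
|---|---|---|---|---|---|
| N=200 | 7% | 22% | 50% | 78% | 95% |
| N=300 | 3% | 18% | 50% | 83% | 98% |

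These are the two ends of the enrolment range in section 5.0. A larger sample drops true values below .3 more often. At N=200 a variable with true r .20 that does pass averages about .33.

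**4. Effect on added R-squared.** This is an assumed illustration: N=200, four sleep measures each with true |r| = .20, common intercorrelation c, five null covariates, 3,000 simulated samples per setting. True added R² = 4(.20)²/(1 + 3c). The average over all samples counts no entry as zero: (1 − share with no entry) × mean among the rest.

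| c | True | No measure enters | Mean where one enters | Mean over all samples |
|---|---|---|---|---|
| .1 | .123 | 77.0% | .116 | .230 × .116 = .027 |
| .3 | .084 | 79.1% | .119 | .209 × .119 = .025 |
| .5 | .064 | 82.2% | .117 | .178 × .117 = .021 |

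Averaged over all samples, the screened figure is far too low. Among the samples where a measure enters, it is too high once c is .3 or more. With all four measures entered and no screen, the sample R² change averages .136, .099 and .082. That is above the truth through ordinary overfitting, so an adjusted R-squared is also needed.

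**5. What the pilot says.** Section 3.0 reports sleep coefficients of about .30 to .47, mixing r, ρ and β, at n=46. A simple correlation there needs |r| ≥ .291 for p < .05. For r = .40, atanh(.40) ± 1.96/√43 gives a 95% CI of about .12 to .62.

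**The case against.** The strongest case on the other side has four parts.

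- **Glycemic control is partly covered.** Equations 2 and 3 are nested if fitted on the same people, so a change in R-squared can be derived. This stands. A reader might infer that no Aim 3 outcome can be answered from the written models; the documents do not support that. The change is nevertheless not planned, and it leaves symptoms and self-management uncovered.
- **Sleep variability is not plainly left out.** The mediation equations list only quantity, quality and timing, which invites that reading. But the hypothesis sentence speaks of sleep health in general, and section 2.0 defines this to include variability. The plural dependent variables also leave room for more than one glycemic measure. The text is inconsistent rather than clearly silent.
- **Where the rule acts is not known.** One might infer that it strips sleep from models of symptoms and self-management. No such models are clearly written. The sentence after the rule, on self-management and glycemic control, may or may not describe the screened regression. Only the general point holds: the rule distorts whichever model it feeds.
- **The pilot coefficients are not below .3.** This is fair against any claim that sleep would usually be excluded. Values of .40 and .47 (p = .006 and .001 as simple correlations) lie well clear of the significance cut and cannot be put down to selection alone; those near .30 may be inflated by it. Several reported β values have p-values that do not match simple correlations at n=46, so the .291 threshold may not apply to them.

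**Conclusion.** The concern holds, and the plan should be changed. That Aim 3 has no planned added-variance analysis follows from the text alone and needs no assumed effect size. That the entry rule is unsuitable follows from its form: it selects on observed size, at more than twice the critical correlation at N=200 (.30 against .139).

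How much the rule costs depends on true correlations that the documents do not give. The loss is large at .20–.25, moderate at .30, and small at .35–.40. The figures take the rule as |r| ≥ .3; read literally with its sign, it would never admit a negative correlation. The four-measure result also assumes equal correlations and covariates that explain nothing. A reader might infer that the screen always inflates added variance, or always shrinks it. Neither is right without saying whether samples with no entry are counted.

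**What to change.** Drop the r ≥ .3 entry rule. Keep the correlations as description and add glycemia to them.

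For each Aim 3 outcome (prespecified symptom measures, self-management, glycemic control, glucose variability), fit a hierarchical regression:

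1. Step 1: covariates named before the data are examined.
2. Step 2: one prespecified measure each of sleep quantity, quality, timing and variability.

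Report each measure's own added R-squared (squared semipartial correlation) with a 95% CI, since Aim 3 names the dimensions as alternatives. Also report the block change in R-squared and adjusted R-squared with a 95% CI. Name one primary outcome and treat the rest as estimates. Keep mediation separate, and call the model from sleep to self-management associational, because the mediation model runs the other way.

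The cost is rewording section 16.0 and restating the power statement with its test, alpha and power; no new data are needed. With nine predictors, alpha .05 and covariates assumed to explain nothing, one measure adding .04 alone has 82% power on its 1-df test at N=200 (94% at N=300), against 61% (81%) on the 4-df block test. The block test reaches 80% power at an added R-squared of .058 at N=200 and .039 at N=300. N for outcomes based on continuous glucose monitoring may be lower, because section 12.0 only asks participants to share those reports.

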duration and timing may be potential therapeutic targets to improve glucoregulation and clinical outcomes (diabetes self-management, diabetes quality of life, neurocognitive function) in this high-risk population. Sleep plays a critical role in physical, mental, social, and emotional health as well as in the effective functioning of the immune system. Short sleep duration is associated with a higher BMI, an impaired body weight regulation and impaired glucose metabolism. COVID-19 has posed barriers for achieving or maintaining healthy sleep. These barriers may include a disruption in daily life, increased anxiety and worry, worsened depression and isolation, a greater family and work stress, and increased screen time. **Preliminary data:** Forty-six young adults with T1D (67.4% female, mean age 22.3 ± 3.2 years, mean BMI 27.0 ± 4.4 kg/m², mean A1C $7.2 \pm 1.1\%$) were recruited from the Yale New-Haven Health System. All study participants (N = 46, 100%) had actigraphy data ranging from 6-14 days/night (Mean 9.0 ± 2.8 days/night) and a majority (n = 43, 93.5 %) had continuous glucose monitor data ranging from 6-14 days/night (Mean 9.5 ± 3.5 days/night). Shorter total sleep time and greater sleep variability were associated with greater daytime sleepiness ($r = -0.47$, $p = .001$ and $r = 0.40$, $p = .005$ respectively). Greater sleep variability was associated with neurocognitive function (longer median reaction time $\rho = 0.31$, $p = .03$ and more lapses $\rho = 0.36$, $p = .01$ on the PVT) and greater glucose variability (mean of daily differences $\rho = 0.33$, $p = .04$). Shorter total sleep time was associated with greater diabetes distress symptoms ($\beta = -0.32$, $p = .032$). Greater sleep variability was associated with greater symptoms of neurological pain ($\beta = 0.32$, $p = .019$) and hypoglycemia ($\beta = 0.32$, $p = .016$). Longer sleep onset latency was associated with greater psychological fatigue symptoms ($\beta = 0.31$, $p = .024$), greater psychological cognitive symptoms ($\beta = 0.37$, $p = .012$), greater hyperglycemia symptoms ($\beta = 0.33$, $p = .024$), and a greater total symptom burden ($\beta = 0.30$, $p = .042$). Poorer sleep efficiency was associated with greater diabetes distress symptoms ($\beta = -0.35$, $p = .018$) and greater hypoglycemia symptoms ($\beta = -0.30$, $p = .027$). The associations between the sleep-wake characteristics and general emotional distress symptoms were not significant. Sex and BMI differences were noted for diabetes symptoms. Specifically, females reported greater hypoglycemia and fatigue symptoms and those with a higher BMI reported greater fatigue, neurological pain, and cardiology symptoms. Associations of these sleep-wake characteristics and symptoms remained statistically significant even after adjustment for sex and BMI.

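### The Aims 2-3 screening rule is written as r ≥ .3 without an absolute value, and even read as |r| ≥ .3 it can remove the sleep dimensions that Aim 3 is meant to evaluate

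*Protocol*

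**What the plan says.** Protocol section 16.0 (Data Analysis Plan), under Aims 2-3, begins: "Correlations between sleep health, diabetes self-management, and symptoms will be assessed". The next sentence is the selection rule: "Variables with a modest relationship ($r \geq .3$) will be included in a linear regression analysis". The section gives no absolute value, no remark on negative correlations and no scoring direction for the scales. It then describes a regression of glycemic control on self-management, and a set of mediation equations that name sleep quantity, quality or timing as the mediator. The power statement in the same section counts two predictors and 4-5 covariates.

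Aim 3 in section 2.0 (Objectives) is to find how much sleep quantity, quality, timing or variability adds to the variance explained in symptoms, self-management and glycemia, in 200 participants.

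Section 3.0 (Background) gives the preliminary results on 46 young adults. For total sleep time it reports: "Shorter total sleep time and greater sleep variability were associated with greater daytime sleepiness ($r = -0.47$, $p = .001" and "Shorter total sleep time was associated with greater diabetes distress symptoms ($\beta = -0.32$, $p = .032". For sleep efficiency: "Poorer sleep efficiency was associated with greater diabetes distress symptoms ($\beta = -0.35$, $p = .018$) and greater hypoglycemia symptoms ($\beta = -0.30".

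The SAP describes a two-group pilot analysed with GEE and does not mention this screen, so it does not clarify the rule.

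**The concern.** A selection rule fixed in advance should give the same variable list whoever applies it. This one does not settle whether a correlation of -.4 passes. Longer or more efficient sleep would be expected to go with fewer symptoms, which is a negative correlation. Sleep variability and sleep onset latency are scored so that higher is worse, and their associations are printed as positive. Followed literally, the rule would sort sleep measures partly by scoring direction instead of strength.

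The second issue does not depend on the sign. Aim 3 concerns the added contribution of named sleep dimensions given other variables. That question is answered by entering those dimensions and reporting their contribution, including when it is small. If a dimension must first reach a bivariate correlation of .3, Aim 3 may be left unanswered for some dimensions. Those that survive will be the ones whose sample correlations happened to be large.

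**Working it through.** **1. Reproducing a printed figure.** Inputs from section 3.0: r = -0.47 between total sleep time and daytime sleepiness, p = .001, and "All study participants (N = 46, 100%) had actigraphy data". With t = r·√[(n − 2)/(1 − r²)]:

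t = -0.47 × √(44/0.7791) = -3.53 on 44 df, two-sided p = .0010. The printed value reproduces.

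**2. Signs of the preliminary associations.** Section 3.0 prints 14 coefficients:

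| Sleep measure | Coefficients | Number negative |
|---|---|---|
| Total sleep time | -0.47 (r), -0.32 (β) | 2 of 2 |
| Sleep efficiency | -0.35 (β), -0.30 (β) | 2 of 2 |
| Sleep variability | 0.40 (r), 0.31, 0.36, 0.33 (ρ), 0.32, 0.32 (β) | 0 of 6 |
| Sleep onset latency | 0.31, 0.37, 0.33, 0.30 (β) | 0 of 4 |

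Of the four negative values, none satisfies r ≥ .3. All four satisfy |r| ≥ .3 if betas are read as correlations, with -0.30 exactly at the cut-off. Counting only the value reported as r, the result is 0 of 1 against 1 of 1.

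**3. Can the betas stand in for correlations?** The same t formula with n = 46 gives:

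- β = -0.32: t = -2.24, p = .030 (printed .032).
- β = -0.35: t = -2.48, p = .017 (printed .018).
- β = -0.30: t = -2.09, p = .043, with a range of .039 to .047 allowing for rounding of the coefficient (printed .027).

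The first two agree within rounding, so they are close to simple correlations. The third is not a simple correlation, and its r cannot be recovered from the documents. Section 3.0 also says "Associations of these sleep-wake characteristics and symptoms remained statistically significant even after adjustment for sex and BMI", without stating whether the printed betas are before or after that adjustment.

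**4. Chance of passing the screen.** By Fisher's z, atanh(r̂) is approximately normal with mean atanh(ρ) and standard error 1/√(n − 3). For n = 200 the standard error is 1/√197 = 0.0712, and atanh(.30) = 0.3095.

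- |ρ| = .47: (0.5101 − 0.3095)/0.0712 = 2.81, P(|r̂| ≥ .3) = .998.
- |ρ| = .35: (0.3654 − 0.3095)/0.0712 = 0.78, P = .784, so it fails 22% of the time.
- |ρ| = .32: (0.3316 − 0.3095)/0.0712 = 0.31, P = .622, so it fails 38% of the time.
- |ρ| = .30: P = .500.

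At n = 150, the lower end of the power statement, the pass probabilities for .47, .35 and .32 are .992, .751 and .606.

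Under the literal rule, a true correlation of -.30 or stronger has a chance below 1e-17 of giving r̂ ≥ +.3 at n = 200. That restates the sign problem and adds no separate evidence.

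**5. How strict is .3?** At n = 200 the two-sided 5% critical value is 1.972/√(198 + 1.972²) = .14. The screen therefore asks for about twice the correlation that would already be statistically significant.

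**The case against.** The best defence is that this is notation. The sentence speaks of a modest relationship, which describes strength; leaving out the bars is common shorthand; and section 3.0 presents negative coefficients as findings of interest. Nothing shows an intention to discard them. That stands, and magnitude is the likelier meaning.

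A reader might go further and infer that the rule removes sleep quantity and efficiency however strong they are, so that Aims 2-3 would show no role for sleep quantity by construction. The documents do not support this, for three reasons.

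- The rule selects variables, not pairs. If self-management is scored so that higher is better, longer sleep could correlate positively with it and enter by that route. The scoring direction is not given.
- The correlations are to be assessed before any screening, so Aim 2 would still show the negative ones.
- The mediation equations name sleep quantity directly, and nothing says the screen governs them.

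The preliminary data are also limited evidence. Three of the four negative values are betas, one of them demonstrably not a simple r. The only one reported as r is with daytime sleepiness, which section 16.0 does not name among the screened constructs.

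Finally, exempting the sleep dimensions goes beyond correcting notation and is not free, since the power statement counts two predictors. This is fair as to cost. The case for the exemption, though, rests on Aim 3 and not on the missing bars.

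**Conclusion.** The point holds in a limited form. The rule is ambiguous as printed. Taken literally it can exclude variables with negative associations, the sign seen for all four printed total sleep time and sleep efficiency results. Correcting the notation would settle that part, and there is no demonstrated analysis error behind it.

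The part with substance is that the screen, even as |r| ≥ .3, can remove exposures that Aim 3 names: about 22% of the time at a true |r| of .35 and 38% at .32, with N = 200. These figures assume that the preliminary betas of -0.35 and -0.32 approximate correlations (supported by their p-values), that similar values hold in the new sample, and that the Fisher approximation applies. They also refer to one correlation at a time. A variable screened against several constructs has more than one chance to enter, so the probability of losing it altogether would be lower.

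**What to change.** In section 16.0, write the rule as |r| ≥ .3 and limit it to candidate variables other than the named exposures. State that sleep quantity, quality, timing and variability enter the Aim 3 models whatever the sign or size of their bivariate correlations.

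No new data are needed and the text change is short. The cost is a few more model terms: four sleep dimensions no longer match a power statement built on two predictors. That statement should be restated with the number of terms actually tested, and the 150-200 sample size checked against it.

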2.0 Objectives

Directions: Describe the purpose, specific aims or objectives. Be sure to also include the hypothesis being tested. The purpose of this study is to characterize sleep health (quantity, quality, timing, variability), diabetes-self-management, symptoms (general diabetes and emotional), and glycemia (glycemic control and glucose variability) over 7 days in young adults age 18-25 years with type 1 diabetes (T1D) during the COVID-19 pandemic. Aim 1. Determine the prevalence of clinically significant emotional distress, diabetes distress, high-risk sleep apnea, and clinically significant insomnia in 200 young adults with T1D and compare to the prevalence of the general T1D population pre-pandemic. Aim 2. Examine the associations between sleep health, diabetes self-management, symptoms, and glycemia in 200 young adults with T1D. Aim 3. Determine the additional contribution of sleep (quantity, quality, timing, or variability) to the variance in symptoms, diabetes self-management, and glycemia in 200 young adults with T1D. Aim 4. Elicit feedback on a behavioral sleep self-management intervention from 10 young adults with T1D who are at low risk for sleep apnea and do not meet the threshold for clinically significant insomnia.

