21.0 Potential Benefit to Research Participants

There is potential benefit to research participants.

Describe the potential benefits that individual research participants may experience from taking part in the research. Include the probability, magnitude, and duration of the potential benefits. *Do not list compensation. Click here to enter text.*

There is no direct benefit to research participants.

If no direct benefit, state the potential benefit to society or others. *Do not list compensation.* There is no direct benefit to participants from participating in this study; however, data from this study could be used to develop meaningful interventions to improve sleep and potentially diabetes related outcomes (glycemic control, decreased symptoms, improved self-management and prevention of premature complications).

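### Section 16.0 lets hyperglycemia and hypoglycemia symptom scores serve as mediators of glycemic control, although such scores reflect glucose; the symptom-adjusted model can then show an indirect effect that does not exist

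*Protocol*

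**What the plan says.** Protocol Section 16.0 (Aims 2-3) states the mediation hypothesis as "sleep health variables or distress (general and diabetes) and physical (diabetes) will mediate the effect of diabetes self-management on glycemic control". Section 2.0 divides symptoms into general diabetes and emotional symptoms, so the physical (diabetes) term is the diabetes symptom set.

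Section 3.0 shows what the team's diabetes symptom scores contain. The preliminary results report "greater hyperglycemia symptoms" and "greater hypoglycemia symptoms", a total symptom burden, and fatigue, neurological pain and cardiology symptoms. There they are analysed as outcomes of sleep.

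Section 16.0 then gives the working rules:

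- Total effect: "A linear regression will be run where the IV is diabetes self-management, and the DVs are glycemic control".
- Decision: "Mediation is present if the independent variable (diabetes self-management) has no effect when the mediator (sleep quantity, quality, timing) is controlled".
- Entry to regression: "Variables with a modest relationship ($r \geq .3$) will be included in a linear regression analysis". The correlations listed for this screen are among sleep health, self-management and symptoms.

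The equations spelled out name only sleep as the mediator. Section 27.0 calls the design cross-sectional, with one data collection for Aims 1-3. Section 12.0 does describe twice-daily surveys for a week, but Section 16.0 plans no lagged or reverse-direction model. The one-page SAP describes a two-group intervention pilot and does not cover this analysis.

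**The concern.** A mediator has to lie between the exposure and the outcome. A score for symptoms of high or low glucose lies on the far side of the outcome: it records what glucose has done. Regressing glycemic control on self-management together with such a score conditions on a consequence of the dependent variable. Part of the self-management association is then absorbed by the score, and the mediation logic reads that loss as an effect transmitted through symptoms.

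At stake is the mediation conclusion of Aims 2-3. The study could report that self-management works on glycemia through physical symptoms when symptoms have no effect on glycemia at all. The direct effect quoted beside it would be too small.

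**Working it through.** **Inputs.** N = 200 is the protocol's target in Section 2.0. The documents give neither the correlation of self-management with glycemia (c) nor that of glycemia with the symptom score (g). Both are assumed: c = -.2 to -.4, g = .3 to .7. Two-sided α = .05 is also assumed, because Section 16.0 states no level. Symptoms are given no effect on glycemia, so true mediation is zero. The plan has no figure of its own on this point to reproduce; its sample-size statement plays no part below except for N.

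**Closed form.** Let self-management be X, glycemia Y and symptoms M, all standardised, in the chain X → Y → M. Then r(X,Y) = c, r(Y,M) = g and r(X,M) = cg. The coefficient of X adjusted for M is

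c' = (c − cg·g)/(1 − c²g²) = c(1 − g²)/(1 − c²g²).

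For c = -.30:

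- g = .3: -.30 × .91/.9919 = -.275, a loss of 8%
- g = .5: -.30 × .75/.9775 = -.230, a loss of 23%
- g = .7: -.30 × .51/.9559 = -.160, a loss of 47%

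The apparent indirect effect equals the loss. At g = .5, the path X to M is cg = -.15. The path M to Y given X is g(1 − c²)/(1 − c²g²) = .5 × .91/.9775 = .4655. Their product is -.070, which is -.300 minus -.230.

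**Simulation.** 5,000 studies per row at N = 200, analysed with the three equations of Section 16.0. The three conditions are: X predicts M; X predicts Y; M predicts Y given X. The strict rule adds that X is no longer significant given M. The last column also requires |r(X,M)| ≥ .3.

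| c | g | c' | Loss | Three conditions met | Strict rule met | Strict rule and screen |
|---|---|---|---|---|---|---|
| -.2 | .3 | -.183 | 9% | 11.8% | 1.7% | 0.0% |
| -.2 | .5 | -.152 | 24% | 27.6% | 7.5% | 0.1% |
| -.2 | .7 | -.104 | 48% | 49.5% | 23.0% | 0.5% |
| -.3 | .3 | -.275 | 8% | 24.7% | 0.3% | 0.0% |
| -.3 | .5 | -.230 | 23% | 57.1% | 1.9% | 0.1% |
| -.3 | .7 | -.160 | 47% | 85.5% | 10.1% | 1.2% |
| -.4 | .3 | -.369 | 8% | 39.0% | 0.0% | 0.0% |
| -.4 | .5 | -.313 | 22% | 80.9% | 0.0% | 0.0% |
| -.4 | .7 | -.221 | 45% | 98.3% | 0.7% | 0.3% |

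Three checks on the reading:

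- With M unrelated to Y (c = -.3), the three conditions are met in 0.3% of runs, so the rates above come from the placement of M.
- A Sobel test of the indirect effect at c = -.3 is significant in 17%, 55% and 85% of runs for g = .3, .5 and .7.
- The mean coefficient of X without M stays at -.30 when c = -.30. The total effect is not biased.

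**The case against.** **The strict rule and the screen give protection.** This largely stands. The plan declares mediation only if self-management has no remaining effect, and that seldom happens once |c| reaches .4. In the assumed chain r(X,M) = cg is at most .28 in size, so an r ≥ .3 screen between self-management and symptoms would usually keep the score out. But Section 16.0 does not say that the screen governs the mediators, or which pair of variables must reach .3. A symptom score could qualify through its correlation with sleep. Even where the strict rule is not met, a path analysis still reports its coefficients.

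**Only sleep appears in the equations.** True, so the consequence is conditional on the symptom model being fitted. The hypothesis those equations are meant to test does name physical symptoms, however, and completing the equations to match it would bring the problem in.

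**No passage says that symptoms follow glucose.** Also true. For hyperglycemia and hypoglycemia symptoms the order rests on what the terms mean. A reader might try to support it from Aim 3, which concerns the "contribution of sleep (quantity, quality, timing, or variability) to the variance in symptoms, diabetes self-management, and glycemia", or from Section 21.0, which lists "glycemic control, decreased symptoms, improved self-management and prevention of premature complications". Neither settles causal order: both also list self-management, which Section 16.0 uses as the independent variable.

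**Physical symptoms are a wider set.** This stands. The documents do not show that fatigue, neurological pain or cardiology symptoms are downstream of glucose, and feedback is possible. The point therefore does not extend to every physical symptom.

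**Conclusion.** The concern holds for the hyperglycemia and hypoglycemia symptom scores and for any total that contains them. It assumes that this study uses symptom scores like those in the preliminary data, and that such scores reflect glycemia without affecting it. On that basis, with c = -.30 and N = 200, the symptom-adjusted self-management coefficient loses about 8% to 47% as g runs from .3 to .7, and the three path conditions are met in about 25% to 85% of studies with nothing mediated. Formal false declarations under the strict rule run from about 0% to 23% over the grid, and to about 1% or less if the screen also gates entry. All c and g values are assumptions; at g = .3 the distortion is small.

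Two stronger conclusions might be inferred and are not supported. The first is that the plan understates the self-management effect altogether: Section 16.0 also runs the regression without the mediator, and that estimate is unaffected. The second is that sleep coefficients in the same models are biased toward zero. That would require sleep to reach symptoms only through glycemia. Section 3.0 reports sleep–symptom associations that may include direct paths, so the direction of bias is not determined.

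This is a wording correction that should be made. It does not undermine the study's other aims.

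**What to change.** In Section 16.0:

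1. Exclude the hyperglycemia and hypoglycemia symptom subscales, and any total symptom score containing them, from the mediators. Exclude them also from the right-hand side of any model for glycemic control or glucose variability, even if they pass r ≥ .3.
2. Analyse these scores as outcomes, as in Aim 3.
3. If other physical symptoms (fatigue, neurological pain, cardiology) are kept as mediators, write out their equations, report the reverse ordering as well (self-management, then glycemia, then symptoms), and state that the cross-sectional data cannot tell the two apart.

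The cost is part of one hypothesised mediator and a little extra analysis; no new data are needed. Removing every physical symptom from the glycemia models would go further than the documents justify, since it would replace one untested ordering with another.
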